Minimization. Although this population may be at high risk for adverse events, it is unlikely that an adverse event will be caused by the research study. Our proposed mobile intervention was developed for people with psychosis and therefore, does not pose the same risks that a pharmacology trial might hold. In the case an Adverse Effect (AE) or a Serious Adverse Effect (SAE) related to the intervention were to occur, a written report of the AE or SAE will be prepared for submission to [name], the Chair of the Butler Hospital IRB. Any such AEs or SAEs will be presented to the full committee of the Butler Hospital IRB as soon as it is feasible. The report of such intervention-related AEs or SAEs will include whether they were expected or unexpected, a rating of severity of the event, a brief narrative summary of the event, whether the informed consent should be changed as a result of the event and whether all enrolled participants should be notified of the event. Finally, as part of the annual progress report (noncompeting continuation application) to NIH, we would provide summary information on all AEs and SAEs that have occurred during that year.

D2. Measures to Ensure Confidentiality

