All data collected by the research team are considered part of the subject's confidential record. Paper data forms collected from research participants will be kept in a locked file cabinet. All data will remain confidential. All data is stored on a secure research server, and backed up daily. Patient identifying information will be stored in a separate database and will be password protected in addition to being on a secure server.

Consistent with requirements by this study's funding source, NIMH, deidentified data will be uploaded to NIMH's NDA twice yearly (January and July) for the duration of the study. Research staff will follow procedures outlined in the NDA, including creating global unique identifiers for each participant to further ensure their confidentiality.

2. Safety Plan and Adverse Event Identification and reporting

Drs. [name] and [name] will be responsible for overseeing the daily safety of all participants. There are several ways in which they will become aware of adverse events. First, research staff will ask patients about serious adverse events (as defined by Office of Human Research Protections (OHRP); e.g., inpatient hospitalization). Second, all study staff will be trained in the OHRP definitions of adverse events that are also unanticipated problems; serious adverse events; or unanticipated problems that are not adverse events. All study staff are required to report any event that might meet one of these criteria to one of the PIs immediately both verbally and in writing. Any report of a serious adverse event will result in one of the PIs contacting the participant to further assess the event.

Adverse Events Definitions

Adverse Event – any unfavorable and unintended sign, symptom or disease temporally associated with the use of a medical or behavioral treatment or intervention regardless of whether it is considered related to the treatment or intervention.

Expected Adverse Event – an event that may be reasonably anticipated to occur as a result of the study procedure and is described in the consent form.

Unexpected Adverse Event – any adverse event which is not described in the consent form and is unanticipated. An event that might have been anticipated but is more serious than expected or occurs more frequently than expected, would be considered an unexpected adverse event.

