Serious Adverse Event- (21 CFR 312) include any untoward medical occurrence that at any dose results in death or the immediate risk of death, hospitalization or prolonging of an existing hospitalization, persistent or significant disability/incapacity or a congenital anomaly/birth defect (NIH guide-6/11/99).

Study Definitions

Specifically, we will consider the following events Serious Adverse Events (SAE):

- a. Death for any reason;
- b. A suicide attempt, defined as any action taken with intent to die, as stated by the patient or noted in the medical record;
- c. Inpatient psychiatric hospitalization

Additionally, we will consider the following events non-serious unanticipated problems:

- a. Evidence of coercion to participate;
- b. Participant distress resulting in stopping of the assessment or intervention;
- c. Access of confidential information by a non-authorized person.

Severity

Each adverse event will be graded in terms of severity:

- a. Non-severe adverse event
- b. Severe adverse event resulting in hospitalization or prolongation of existing hospitalization, a persistent or significant disability/incapacity.
- c. Life-threatening adverse event
- d. Fatal adverse event

Attribution

For each adverse event, one of the following attributions is assigned:

- Definite: Adverse event is clearly related to intervention
- Probably: Adverse event is likely related to intervention
- Possible: Adverse event may be related to intervention
- Unlikely: Adverse event is doubtfully related to intervention
- Unrelated: Adverse event is clearly not related to intervention

Suicidality. Because we will be recruiting individuals with psychiatric disorders, we may have some participants who disclose having suicide ideation or behavior. At the time that suicidality is identified by any study staff member for in-person assessments, they will contact a study clinician who will immediately evaluate that person. All study staff (e.g., research assistants) are trained in the Psychosocial Research protocol for managing suicidality. All clinical faculty in our research group, including Drs. [name] and [name] are experienced in management of suicidality and other clinical emergencies. Drs. [name] and [name], both licensed psychologists, will be available during regular business hours. After hours there is always a licensed

mental health clinician (psychologist or psychiatrist) available on call by cell phone or pager in the Psychosocial Research Program.

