Both MPIs and the DSMB Chair will develop the Data Safety Monitoring Plan. It will then be circulated to the rest of the DSMB for feedback and approval. The board members will review the initial DSMB protocol to ensure that it captures the information necessary to evaluate the safety and efficacy of the study. The DSMB will then receive DSM reports bi-annually. A DSM report will include concerns about significant safety and data monitoring issues such as recruitment, retention, and quality of data collected.

Operating procedures of the DSMB include monitoring the protocol to evaluate the safety of the participants as pre-specified in the DSMP of the protocol, monitoring efficacy of the intervention being tested, and evaluating performance of the trial, as well as study admission data and protocol compliance. The specific content of the reports to the DSM include information about AEs and/or SAEs, treatment retention, recruitment, reasons for dropout, and interim efficacy data.

Only reports that meet the criteria of being a death (within 5 calendar days) or SAEs that are unexpected/related to study procedures (within 10 calendar days) will be reported to the DSMB within the specified timeframe after learning of the event. Summary reports of all adverse events will be provided to DSMB in bi-annual reports. Finally, as part of the annual progress report (noncompeting continuation application) to NIH, we would provide summary information on all adverse events that have occurred during that year.

As they deem necessary, the members of the DSMB will evaluate whether the presence of early unanticipated therapeutic results, side effects or adverse consequences are significant enough to warrant amendment, suspension, or early termination of the study and will independently make recommendations to the PIs to continue, to amend or to terminate the trial. Recommendations related to the study will be made in a written DSMB Report by the Board's Chairperson to the Principal Investigator and this DSMB Report, along with the DSMB meeting minutes, will be sent to the NIH Project Officer for the study.

E. Potential Benefits

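### The DSMB and NIH are promised summaries of all adverse events, but patients are asked only about serious ones and no rule turns symptom or app data into adverse event records

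*Combined protocol and SAP*

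**What the plan says.** **What is promised.** Section D3 part 3 (Data and Safety Monitoring Board) states: "Summary reports of all adverse events will be provided to DSMB in bi-annual reports". For the annual NIH progress report it adds: "we would provide summary information on all adverse events that have occurred during that year". Section D1, under Risk of adverse events, makes the same commitment to NIH: "we would provide summary information on all AEs and SAEs that have occurred during that year". D1 also promises the IRB a written report of any intervention-related AE, serious or not.

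**What counts as an AE.** Section D3 part 2 defines it as "any unfavorable and unintended sign, symptom or disease temporally associated with the use of a medical or behavioral treatment or intervention", whether or not it is thought to be related. The severity scale begins with "Non-severe adverse event", and each AE is to be given an attribution.

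**How events are found.** D3 part 2 gives two routes. The first is "First, research staff will ask patients about serious adverse events"; the study's own SAE list is death, suicide attempt and inpatient psychiatric admission. The second is staff reporting: all staff are to be "trained in the OHRP definitions of adverse events that are also unanticipated problems; serious adverse events; or unanticipated problems that are not adverse events", and must pass on anything that might fall into one of those classes. One of the listed non-serious problems is "Participant distress resulting in stopping of the assessment or intervention".

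**The concern.** The promised summary is wider than the stated collection. A non-serious AE that is not an unanticipated problem is not asked about, and it is not in a class that staff must report under D3 part 2. The definition, the non-severe grade and the attribution scale all imply that such events will be recorded.

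Two things are at stake. First, D3 part 3 asks the DSMB to judge whether side effects or adverse consequences justify changing or stopping the study. A short AE list could mean little harm or little asking, and the board could not tell which. Second, section A presents the pilot as preparation for a full-scale trial, so its AE record is likely to be carried forward into that trial's planning. The harms most specific to a prompting app (burden, unease about being monitored, upset that falls short of stopping) are the least likely to surface.

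**Working it through.** The documents give no AE rate, and no power or sample-size figure tied to AEs, so there is no stated number to reproduce. The check has two parts.

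**1. Can each route carry a non-serious AE into the AE record?**

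| Route | Where | What it picks up | Link to an AE record |
|---|---|---|---|
| AE question to patients | D3 part 2 | Serious events only | Yes, for SAEs |
| Staff reporting duty | D3 part 2 | SAEs; unanticipated problems, whether AEs or not | Yes, for those classes |
| Staff who see or are told of an AE contact the investigators, who complete a form | D3 part 2, Adverse Event Reporting | Whatever comes to notice | Yes, but passive |
| BPRS at baseline and months 1, 2 and 4; interviewer checks for suicide risk and deterioration | Table 1; D1 | Symptoms, both arms | Only if psychotic items are rated above 5, or for significant suicidal or homicidal risk (D1) |
| App items on affect, psychosis, functioning, substance use and safety | C3 | Repeated self-report, same items in both arms | Weekly review for safety risk; no AE logging rule |
| End-of-treatment interview, months 1 and 4 | Table 1; C3 | What patients disliked about the app and the study | None stated |

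Table 1 has no AE form, no AE recall period is given, and C4 (Data Analysis) plans no AE tabulation. Two kinds of event have no dependable path to the record: harm that the symptom measures do not cover, and worsening that is measured but stays below the D1 triggers.

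**2. What would a low count mean? (illustration only)**

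Inputs: 80 patients randomised (section A). The allocation ratio is not stated, so n = 40 per arm is an assumption. The capture probability *c* (the chance that an event reaches the record) is also assumed, and so is the true risk of 5%.

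- One-sided 95% upper limit for 0 of 40 recorded: 1 − 0.05^(1/40) = 0.0722.
- Implied limit for the true risk: 0.0722 / *c*. This is 7.2% at *c* = 1, 14.4% at 1/2, about 22% at 1/3 and 28.9% at 1/4.
- Chance of recording at least one event in 40 when the true risk is 5%: 1 − (1 − 0.05*c*)^40. This is 87% at *c* = 1, 64% at 1/2 and 40% at 1/4.
- With equal true risks, the recorded MACS:control ratio equals the ratio of the capture probabilities. Capture of 50% against 40% gives 0.50/0.40 = 1.25, 50% against 25% gives 2.0, and equal capture gives 1.0.

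The last line shows what unequal capture would do. It is not evidence that capture is unequal here.

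**The case against.** **Patients are asked about much more than serious events.** This is largely right. BPRS, WHODAS-2, AUDIT and DUDIT are repeated at every follow-up, every app session asks about suicide risk and psychotic symptoms, and the items are the same in both arms. A reader might infer that nobody is asked about non-serious harm, and the documents do not support that. What remains is narrower: only the AE inquiry is limited to serious events, and outside the D1 triggers nothing says when the other data become AEs.

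**The end-of-treatment interview already invites complaints.** It does, at months 1 and 4. But it is listed as feedback, is not held at month 2, and has no stated link to AE recording.

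**Staff must escalate AEs that they see or hear of.** They must, with a form giving severity and attribution. This softens the gap without closing it: the step is passive, and its lead-in speaks of the listed possible events and other unanticipated ones.

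**Bias between arms is speculation.** A reader might infer that MACS events will be noticed more often, or that any difference in AE counts would reflect contact and not harm. The documents show neither. The MACS-only clinician meeting is planned before discharge where possible, so it falls largely before app exposure. The later MACS-only provider reports draw on app items that both arms answer, and C4 plans no AE comparison between arms. Only a possibility remains, through the meeting, the provider reports and an inconsistency over who reviews app data each week (the study clinician as part of report writing in D1; research staff in C3 and D3).

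**All AEs may mean all AEs recorded, which is reasonable for a minimal-risk app.** On that reading the promise is kept by construction, but the summary still cannot show whether a short list reflects little harm. It is also fair that C4 puts feasibility and acceptability first, so the pilot should not be read as a formal safety clearance.

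**Conclusion.** The mismatch is real, though narrow. The protocol promises summaries of all AEs under a broad definition, solicits only serious ones, and relies on passive notice and two high-threshold triggers for the rest. Non-serious harm outside those routes is likely to be under-recorded, and a low AE count would be hard to interpret. Capture could differ by arm; neither the presence nor the size of such a difference can be estimated from the documents.

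The size of the under-recording cannot be estimated either. The limits of 7.2%, about 14% and about 22% for zero events in 40 only show how fast a reassuring statement weakens as capture falls. They rest on an assumed 40 per arm and assumed capture of 1, 1/2 and 1/3. Full capture is itself an ideal that a single open question may not reach.

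This should be fixed because it is cheap and affects what the DSMB can conclude. It does not undermine the feasibility and acceptability aims.

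**What to change.** **Preferred: collect what is promised.**

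- At the existing month 1, 2 and 4 assessments, in both arms and with the same script and recall period, ask one open AE question, plus one item on whether the app or any study procedure upset the patient or made anything worse.
- State when a BPRS or app response is logged as an AE. The investigators should set that rule.
- Record all AEs whatever their seriousness. Tabulate them by arm and by how they were found (asked, measured, volunteered or noticed by staff).
- Reconcile C3, D1 and D3 on who reviews app data each week, and say whether this is the same in both arms.

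**Alternative: promise what is collected.** Restate the NIH sentence in D1 and the DSMB and NIH sentences in D3 part 3 as covering only SAEs and unanticipated problems, and say that other AEs are not systematically sought.

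**Cost.** The preferred route takes a few minutes per visit, one form and a short amendment. It will produce more AE forms and a higher AE count, which should be explained to the DSMB in advance. The alternative costs only an edit, but leaves non-serious harm unmeasured.

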5D. PHI is only needed for activities preparatory to research

YES NO

6) DESCRIPTION OF PHI TO BE COLLECTED UNDER WAIVER

Chart reviews of new patients will be routinely conducted by study staff to determine if they are likely to meet inclusion/exclusions criteria for the study as described above. PHI to be obtained: patient demographic and contact information (name, address, telephone numbers, gender, age, race, marital status, occupation status) and patient psychiatric/treatment history (diagnoses and suicide history, past and current psychological and/or pharmacological treatments, current mental health provider contact information, lab results).

7) ADVERTISEMENTS

Study brochure; see attached.

8) INFORMED CONSENT FORM (ICF), ASSENT OF MINOR & PARENTAL PERMISSION FORM

See attached.
